### **Secondary Objectives**

- To determine changes in haemoglobin in blood donors over a 6-month period.
- To determine the impact of iron supplementation on the change in haemoglobin.
- To estimate the prevalence of ID and IDA in prospective first-time blood donors.
- To determine the factors associated with ID and IDA among prospective blood donors.
- To determine the prevalence of malaria or adverse events among the prospective first-time blood donors.
- To identify the barriers and facilitators of repeat donation and the use of dietary and iron supplementation interventions to address ID and/or anaemia among blood donors.
- To determine feasibility of the intervention, through documenting implementation fidelity, intervention adaptation, and intervention strengths and weaknesses.
- To understand participant and key informant acceptance of the intervention.
- To develop and implement key strategies aimed at increasing the blood donor pool.

- To compare haemoglobin levels as determined by copper sulphate versus automated haematology analyser.

## Duration

The duration of this UG3 phase (Pilot trial) is 1 year.

## Sample size

**Qualitative study:** In all, ten focus groups of 8-10 participants purposively selected with one group from each of the following blood donation categories: (i) religious organizations, (ii) educational institutions, (iii) corporate institutions, (iv) organized community groups, and (v) walk-in blood donors. The aim of the focus groups is to identify barriers and recommendations for using iron supplementation and nutritional counselling to increase the blood donor pool. These discussions may involve gender-sensitive topics and gender may impact participation in the discussion, so two groups of each blood donation category by gender will be formed (e.g., 8-10 females, 8-10 males). The female and male focus groups will meet in separate spaces so only one gender will be interviewed at a time. Thus, there is one male and one female group for each donation category.

**Quantitative method:** Cross-sectional study to determine the prevalence of anaemia among prospective blood donors: There are 2 distinct components of the cross-sectional study: estimation of the proportion of potential donors deferred due to low haemoglobin and the proportion of first-time potential donors who have ID and IDA. The determination of deferral due to low haemoglobin is routinely collected by the National Blood Service Ghana (NBSG) and does not require consent of potential donors in this study. The proportion deferred will be determined using the same donation sites as the other components of the study with an estimated sample size of 600 and resulting margin of error less than 0.04. Consequently, the 95% confidence intervals for deferral prevalence will have a total width of less than 0.08 giving a more precise estimate than the year-to-year variation in the total percentage deferred. Participant consent is needed to draw blood for determination of ID and IDA. We anticipate that 292 participants will consent and be enrolled with resulting margin of error less than 0.057 and total confidence interval width of less than 0.11 for likely values of the prevalence of ID and IDA among first-time potential donors (conditional on deferral status). Thus, the ID and IDA prevalence estimates will have comparable precision to the estimated proportion of those deferred using all potential donors at recruitment sites.

Parallel groups' trial to assess the acceptability of iron supplementation: Using a non-inferiority design with a non-inferiority margin of 1 g/dL for haemoglobin levels at 4 months, a 1-sided alpha level of 0.025, at least 85% power and under the assumption that the true difference in the means is 0.3 requires 262 participants (131 per arm). This number has been increased to allow up to 10% loss to follow-up or iron supplementation for those initially not requiring supplements (such individuals will be excluded from the primary analysis: see Section 7.2.1 for further details), thus the sample size is 292. For efficiency, participants will be enrolled into both parts of the quantitative study.

## **Study site and Population**

The NBSG SZBC located in the capital Accra annually collects voluntary blood donations from 200-300 blood donor groups that are categorized as (i) religious organizations, (ii) educational institutions, (iii) corporate institutions, (iv) organized community groups, (v) walk-in blood donors and (vi) mass/media events. Data for the prevalence of deferral assessment will be collected from all prospective voluntary blood donors within the catchment areas of the SZBC. The prevalence study of ID and IDA as well as the parallel groups trial will be restricted to first-time donors. The parallel groups trial will be restricted to voluntary donors. Generally, prospective voluntary blood donors are healthy, unlikely to be severely anaemic and are more likely to be male.

The study population will be all adults between the ages of 17 and 60 years who visit blood donation sites at the time of recruitment. A stringent screening and selection process is performed to evaluate the suitability of prospective donors. This is essential to guarantee the safety and adequacy of the blood supply; protecting the wellbeing of the recipients of transfusion as well as the fitness of the donors while ensuring that qualified donors are not deferred needlessly.

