Out of the sampling frame, participants will be purposively sampled for Focus Group Discussions (FGDs). In all there will be ten FGDs i.e. two groups (male-only and female-only) randomly selected to represent each of the five NBSG voluntary blood donation categories (excluding mass/media event donors), and with each group composed of both first-time and repeat donors. In-depth interviews will also be conducted with blood donation staff and medical officers responsible for blood donation.

Regimen

The prevalence study will be conducted over the first 6 months of the study period. For the cross-sectional deferral assessment, all donation attempts and deferrals from sites where recruitment for the parallel groups study will take place will be recorded. The number of deferrals among first-time donors will also be determined. Potential first-time donors will be asked if they are interested in participating in a study of the prevalence of ID and IDA and the impact of iron supplementation on haemoglobin levels and repeat donation. Those who express interest and consent to the study will be asked to return in approximately 2 weeks. During this 2-week period a full blood count (FBC) and plasma ferritin measurement will be determined, and participants will be classified as ID, IDA or otherwise (which we refer to as controls in this protocol). Those found to be ID or IDA will receive oral

iron supplementation and nutritional counseling. Controls will not be given iron supplementation but will receive the standard practice of nutritional counseling for blood donors. Additional baseline data will be collected at the 2-week return visit. The duration of the intervention period is 4 months with two interim visits (approximately 2 months apart) and a final visit at 6 months. A blood draw will be conducted for a FBC, peripheral film comment, malaria rapid test and ferritin measurement at both interim visits and the final visit. Participants will receive bi-weekly follow-up phone calls for adherence and monitoring for adverse events. Qualitative assessment of acceptability of oral iron supplementation among donors previously deferred will be performed during the final month of the pilot study.

Inclusion Criteria

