## **3 Study Population**

### **3.1 Eligibility**

#### **Inclusion Criteria**

There are 3 components of the quantitative study (observational study of deferral, observational study of the prevalence of ID and IDA, and the parallel groups trial of iron supplementation) with slightly different inclusion and exclusion criteria, hence we indicate which criteria apply to which component of the study below.

Items 1-3 are required for the observational study of deferral, items 1-4 are required for the observational study of the prevalence of ID and IDA and items 1-6 are required for the trial. Only participants who meet ALL the following inclusion criteria will be eligible for the trial:

- 1) Males or females aged between 17 and 60 years who weigh at least 50kg.
- 2) Pass pre-donation screening using the NBSG standardised donor screening questionnaire for medical conditions and lifestyle risks for transfusion transmissible infections (TTIs) (Appendix 5).

- 3) Vital signs must meet the NBSG requirement for blood donation: systolic and diastolic blood pressures between 90-140 mmHg and 60-90 mmHg, respectively; pulse rate between 50-100 bpm; non-contact forehead temperature not exceeding 37.5°C; meeting acceptable requirements for skin lesions, needle marks and physical appearance.
- 4) Must be willing and able to give study consent or assent.
- 5) Intend to remain in the study location/site during the entire length of the study.
- 6) Voluntary non-remunerated blood donor

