### 3.3 Analysis population

The analysis population for the anaemia deferment study will include all eligible participants, while the analysis population for the ID/IDA study and the trial will include all eligible and consented participants.

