### 3.4 Baseline characteristics

Baseline characteristics for those who enrol in the trial will come from information collected on the screening and enrolment forms. The only characteristics captured for those in the anaemia deferment study are age, sex, if the person has previously donated, and the type of donation (i.e., replacement/family or voluntary). For those in the study of ID/IDA information on abnormal peripheral blood film, malaria, haemoglobin, ferritin, and TTI status will also be obtained. Additional information will be available for those in the trial. For the open report, baseline characteristics will be summarized pooled across the two treatment groups and presented separately for those in the anaemia deferment study, the ID/IDA study, and the trial. Note that these study populations are related as follows: everyone in the trial is in the ID/IDA study, and everyone in the ID/IDA study is in the anaemia deferment study. Note that someone who consents to the trial but is found to have levels of haemoglobin that are too low at screening will participate in the ID/IDA study but will not participate in the trial.

For the closed report, baseline characteristics will be summarized by treatment group for the Iron Supplementation Trial.

The following baseline characteristics will be summarized with counts and percentages for binary and categorical variables, medians and quartiles for continuous variables and ordinal variables when available for each of the 3 components of the study.

Demographics:

- Age: summary as continuous variable.
- Sex.
- First-time donation status (Yes or No).
- Number of children (an integer equal or above 0).
- Marital status (6 options).
- Home situation (6 options).
- Main method of travel (private or public).
- Highest level of education completed (7 options).
- Employment category (8 options).
- Number of expensive, durable consumer items (an integer in the range 0-7).
- Ethnic background (6 options).
- Religion (5 options).

Screening laboratory results:

- Haemoglobin concentration.
- Plasma ferritin concentration.

- Malaria test results from a malaria rapid diagnostic test.
- Abnormal peripheral blood film results reported by type of abnormality (i.e., helminthic infection, malaria, neutrophilia, leucocytosis, and lymphocytosis).
- ID present
- IDA present.

Medical History:

- Diagnoses (19 options, select all that apply).

Nutritional History:

- Number of meals yesterday (4 options).

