## **7 Quantitative Data Analysis**

### **7.1 Cross-sectional study**

Analytical approaches to the analysis of data from the prevalence study will focus on univariate summaries but will also investigate risk factors for deferral. An exact

confidence interval for the probability of deferral will be computed using the method first described by Clopper and Pearson. Logistic regression will be used to assess risk factors for deferral. These risk factors will include age, sex, previous donation status and type of donor.

Since recruitment at donation events focuses on informing individuals who fail the copper sulphate test about the study, we expect that the proportions of those who are ID and IDA will be higher than the proportion among those attending a donation event. For this reason, we will estimate the level of ID and IDA overall by weighting the estimates within deferral strata by the observed probability of deferral based on the cross-sectional study of deferral (but restricted to first time donors, or voluntary first time donors depending on who enrolls into the ID/IDA study). To obtain 95% confidence intervals for the overall proportion of those who are ID and IDA we will use a Bayesian approach in which we sample the probability that first-time donors are deferred for low haemoglobin from its posterior distribution (which is a beta distribution) and we sample the probability of being ID and IDA conditional on deferral status from their posterior distributions (which will also be beta distributions). We can then combine these draws from the posterior distributions to obtain weighted estimates of the probability of being ID and IDA that will be consistent for these probabilities in the overall population. Risk factors for being ID and IDA conditional on the outcome of the copper sulphate test will be examined using logistic regression.

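### The deferral study is stated to cover voluntary donors, but the SAP's criteria and single unrestricted deferral estimate would pool family replacement donors with them

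*SAP*

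**What the plan says.** **Stated population.** Study site and Population, in both the protocol and SAP 1.2, defines the deferral population by donor type: "Data for the prevalence of deferral assessment will be collected from all prospective voluntary blood donors", within the centre's catchment.

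**Eligibility.** SAP 3.1 says: "Items 1-3 are required for the observational study of deferral". Those items are age and weight, the donor questionnaire, and vital signs. Being a voluntary, non-remunerated donor is item 6, and only the trial requires items 1-6. The protocol's criteria do not list voluntary status for any component.

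**Analysis population.** SAP 3.3: "The analysis population for the anaemia deferment study will include all eligible participants".

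**Variables.** SAP 3.4 names four characteristics captured in the deferral study. One of them is "the type of donation (i.e., replacement/family or voluntary".

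**Analysis.** SAP 7.1 plans one Clopper-Pearson interval for the probability of deferral, then logistic regression for risk factors: "These risk factors will include age, sex, previous donation status and type of donor". It restricts to first-time donors, or voluntary first-time donors, only where the deferral probability is used to weight the ID and IDA estimates.

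**Denominator.** The Regimen section of the protocol says: "For the cross-sectional deferral assessment, all donation attempts and deferrals from sites where recruitment for the parallel groups study will take place will be recorded". SAP 2.4 has every potential donor contributing to the estimate and sizes the study at about 600 donation attempts. SAP 3.1 says that people are tracked only if they meet the eligibility criteria.

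**The concern.** A statistician following SAP 3.1, 3.3 and 7.1 would put every record meeting items 1-3 into one proportion, replacement donors included. A reader of Study site and Population would take that proportion to describe voluntary donors.

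Estimating deferral is a named component of the study, and SAP 2.4 intends to compare the result with yearly rates. The protocol's Problem Statement shows that those rates (33-53%) concern voluntary donors. The project aims to enlarge the voluntary pool, so the useful figure is the one for voluntary donors. If replacement donors are deferred for low haemoglobin at a different rate, the pooled proportion answers a different question, and its interval gives no sign of this.

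**Working it through.** **1. Which population the text implies**

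| Place | Donor type | Denominator |
|---|---|---|
| Study site and Population (protocol; SAP 1.2) | voluntary only | all prospective donors in the catchment |
| Protocol, Regimen | not restricted | all attempts at recruiting sites |
| SAP 2.4 | not restricted | all potential donors, about 600 attempts |
| SAP 3.1 and 3.3 | not restricted (item 6 is for the trial) | those meeting items 1-3 |
| SAP 3.4 and 7.1 | both types recorded and modelled | as SAP 3.3 |

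Type of donor can be a risk factor only if both types are in the data. SAP 1.2 also adds a separate sentence limiting the trial to voluntary donors, which would be unnecessary if every component already had that limit. The operative sections therefore admit replacement donors.

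**2. The plan's own precision**

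Margin = 1.96 × √(p(1−p)/n). With n = 600 and p = 0.2, 0.3, 0.4, 0.5, 0.6 this gives 0.032, 0.037, 0.039, 0.040, 0.039, which matches Table 1. The arithmetic is right; the open question is whom the 600 represents.

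**3. Margin if only part of the 600 are voluntary**

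Let w be the replacement share of the records (assumed, because no document gives it). Voluntary n = 600 × (1 − w), with p = 0.5.

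| w | voluntary n | margin |
|---|---|---|
| 0 | 600 | 0.040 |
| 0.10 | 540 | 0.042 |
| 0.30 | 420 | 0.048 |
| 0.50 | 300 | 0.057 |

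**4. Shift from pooling**

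Pooled rate = (1 − w) × voluntary rate + w × replacement rate, so the shift is w × D, where D is the difference between the two rates. The documents give neither w nor D for these sites. Purely as illustration:

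- D = 10 points: 1, 3 and 5 points at w = 0.10, 0.30 and 0.50. The shift passes 0.04 only when w exceeds 0.40.
- D = 5 points: 0.5, 1.5 and 2.5 points at the same shares.

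The direction depends on the sign of D, which is also unknown.

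**5. The yearly comparator**

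The 33-53% in the Problem Statement is the share of *deferred* voluntary donors whose deferral was for low haemoglobin. SAP 2.4 treats it as an annual proportion of deferrals and compares it with a proportion of *donors*. Even a voluntary-only estimate would therefore have a different denominator.

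**6. The pre-screen**

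Let e be the share of attempts failing items 1-3 (not given). If low-haemoglobin deferral is counted only among those who pass, the all-attempts proportion is p × (1 − e). An assumed p of 0.30 becomes 0.27 at e = 0.10 and 0.24 at e = 0.20. The two quantities differ, so the label matters.

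**The case against.** Three points on the other side have weight.

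**Donor type is recorded.** A voluntary-only rate needs no new data, and SAP 7.1 already allows a voluntary restriction for the ID/IDA weights. This stands, and it makes the repair cheap. It does not settle which proportion will be reported, since the SAP names only the unrestricted one.

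**The pre-screen is open and sensible.** A reader might infer that requiring items 1-3 makes the estimate wrong. The documents do not support that. Both eligibility sections state the restriction, SAP 3.3 repeats it, and SAP 1.2 makes eligible people the sampling frame. Low-haemoglobin deferral among donors otherwise fit to donate is a legitimate target for an iron programme. Recording all attempts is also compatible with analysing only eligible people. What remains is a conflict of wording with the Regimen section and SAP 2.4.

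**The size is unknown.** A reader might take the protocol's figure of over 66% replacement collection as the replacement share here, and conclude that about 204 of the 600 records are voluntary (600 × 0.34), with a margin of 0.069, or that the bias exceeds 0.04. The 66% is a share of national blood collection. The recruitment sites serve voluntary donor groups, where the share may be small. The 600 rests on an assumed five attempts per business day, while the centre saw about 550 prospective voluntary donors a week (550 × 26 = 14,300 in six months), so voluntary numbers need not limit precision. No document gives a deferral rate for replacement donors.

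**Conclusion.** The donor-type conflict is in the current text and would change what is reported. The stated population is voluntary donors; the estimate that SAP 7.1 specifies is not restricted to them and is not like for like with the voluntary-donor yearly figures.

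The size of the pooling shift cannot be determined, because it needs a site-level replacement share and a difference in deferral rates that the documents do not give. The illustrative shifts and wider margins rest on assumed values. A claim that the shift exceeds the planned margin of error is not supported.

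The items 1-3 restriction is a labelling matter, not a flaw in the estimand. Nothing here touches the trial's primary analysis, and the ID/IDA weights already allow for donor type.

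**What to change.** **Main change.** In SAP 3.3 and 7.1, define the deferral proportion and its exact interval for voluntary donors only. Report replacement donors separately, using the donor type already recorded. State the Table 1 margin for the expected voluntary count.

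**Comparison with yearly rates.** In SAP 2.4, say that the 33-53% has deferred donors as its denominator. Either compute the matching share or drop the direct comparison.

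**Secondary.** Label the estimate as low-haemoglobin deferral among donors passing items 1-3. Reconcile the protocol's Regimen section and SAP 2.4 with SAP 3.1 and 3.3. Where the blood service's routine counts allow, also tabulate low-haemoglobin deferrals over all voluntary attempts.

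**Cost.** SAP wording and one tabulation by donor type. The margin widens if some of the 600 records are replacement donors, unless collection continues to 600 voluntary records. The all-attempts table depends on usable counts of people failing items 1-3, which the SAP does not currently plan to track.

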## **Stratification and Sampling**

The SZBC contributes to the blood service needs of the Western, Central, Greater Accra, Eastern and the Volta Regions of Ghana. In 2018 and 2019, the SZBC attended to an average of 550 prospective voluntary blood donors a week, including 80 walk-in donors. Out of this number, the study will recruit all participants (who fall within the inclusion criteria) reporting per day for up to 6 months until the sample size is attained. Eligible participants will form the sampling frame for the study.

Donors will be informed about the trial and the prevalence study of ID and IDA. Due to a need to recruit approximately equal numbers of participants in the 2 groups in the trial, donors who fail the copper sulphate test will be disproportionately approached for participation. This creates a stratification of donors by status with regard to the outcome of the copper sulphate test. Within these strata the proportion of donors who are ID and IDA will be determined. The estimates of these proportions within strata will be unbiased but if one simply averages over the strata, we expect that the estimates of the proportion who are ID or IDA will have positive bias. However, since we will have estimates of the proportion of donors who fail the copper sulphate test, we can post-stratify the proportions of donors who are ID or IDA by the proportion of donors who fail the copper sulphate test.

Out of the sampling frame, participants will be purposively sampled for FGDs. In all there will be ten FGDs i.e., two groups (male-only and female-only) selected to represent each of the five NBSG voluntary blood donation categories (excluding mass/media event donors), and with each group composed of both first-time and repeat donors. In-depth interviews will also be conducted with blood donation staff and medical officers responsible for blood donation.

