**Table 1: Precision of prevalence estimates for low haemoglobin leading to deferral.**

Prevalence	Error Margin	95% Confidence Interval
0.2	0.032	0.17, 0.23
0.3	0.037	0.26, 0.34
0.4	0.039	0.36, 0.44
0.5	0.040	0.46, 0.54
0.6	0.039	0.56, 0.64

Since not all participants will consent to participate in the study and only a subset of donors are first-time donors, the precision of estimates of the prevalence of ID and IDA will be lower. Based on the unpublished estimates of the prevalence of ID and IDA provided above (i.e., 63.9% of those with anaemia had IDA and 86.1% of those with anaemia had ID, so 30.7% of the total had IDA and 41.3% had ID), estimates of the prevalence of these conditions cover almost the same range as our estimates of the prevalence of low haemoglobin. Since enrolment for this component of the study entails enrolment in the longitudinal study, the sample size was determined by the requirements for the longitudinal study which is 292 participants. Since some participants in the cross-sectional study of ID and IDA may be found to have haemoglobin (Hb)<10g/dl and will therefore be excluded from the longitudinal study, the sample size for the cross-sectional study may exceed 292. This will require that, on average, almost 2.5 participants per day consent to the study to get to about 300 over the 6-month enrolment period. Table 2 shows values for the prevalence of ID/IDA within deferral strata, the corresponding margin of error and the corresponding 95% confidence interval. For example, if the prevalence of IDA is 30% within one of the strata then a 95% confidence interval would be (25%, 35%) which has a total width comparable to the confidence intervals obtained using all potential donors. The intervals for the post-stratified estimates will be slightly larger due to the sampling variability of the estimated post-stratification weights.

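### ID/IDA prevalence is called unbiased and consistent without condition, but it is weighted only on the copper sulphate result; it can be biased if consent and iron status both differ by sex, which is already recorded.

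*SAP*

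**What the plan says.** SAP 1.2 (Stratification and Sampling) recognises one way in which the ID/IDA sample departs from the donors who attend: "donors who fail the copper sulphate test will be disproportionately approached for participation". It then says of the resulting strata: "The estimates of these proportions within strata will be unbiased". It expects bias only from averaging over the strata without weights.

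SAP 7.1 gives the estimator: "we will estimate the level of ID and IDA overall by weighting the estimates within deferral strata by the observed probability of deferral", with the deferral probability restricted to first-time (or voluntary first-time) donors. Intervals come from beta posterior draws for the deferral probability and for ID/IDA within each stratum. The combined estimates are described as ones "that will be consistent for these probabilities in the overall population".

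Three further places bear on this:

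- SAP 2.4 accepts incomplete participation: "Since not all participants will consent to participate in the study". It plans on about 300 consenters, against about 600 donation attempts.
- SAP 3.4 lists what is known about the weighting population: "The only characteristics captured for those in the anaemia deferment study are age, sex, if the person has previously donated", plus type of donation. It adds that "everyone in the ID/IDA study is in the anaemia deferment study". Sex is therefore known for consenters and non-consenters alike.
- SAP 2.6 puts a table of deferment-study baseline characteristics by consent status in the open DSMB report. Nothing in SAP 7.1 uses that table.

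**The concern.** Stratifying on the copper sulphate result corrects for the unequal approach that the study itself creates. It does not correct for who agrees. Consent here means joining a 6-month study with return visits, and no random selection of consenters within a stratum is described for the prevalence study. The random selection mentioned in SAP 1.2 (Design) balances the trial groups and does not make consenters representative of attenders.

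Sex is the obvious variable to check. The protocol's background gives anaemia as 42.4% in women of reproductive age and 18.8% in peri-urban men, and notes that one donation removes a large part of a woman's iron stores. If women and men consent at different rates, and their ID prevalence differs within a stratum, the stratum estimate moves towards the over-represented sex. Weighting the strata by deferral leaves that shift in place. At stake are the centring and coverage of the ID and IDA prevalence intervals, which serve a named study component and a secondary objective. The primary haemoglobin comparison is not affected.

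**Working it through.** **The plan's own figure.** SAP Table 2 gives margins of 0.046, 0.053, 0.056 and 0.057 at prevalences 0.2, 0.3, 0.4 and 0.5. The formula 1.96 × √(p(1−p)/292) gives 0.0459, 0.0526, 0.0562 and 0.0573, so the table reproduces at n = 292. SAP 2.4 describes it as precision within deferral strata, but 292 is the total. With 146 per stratum (an assumed equal split) the same formula gives 0.065 to 0.081. Coverage for one stratum therefore needs the n = 146 standard error.

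**Bias formula.** Within one stratum, let f be the female share of attenders, R the female:male consent ratio, and pF and pM the ID prevalence in women and men.

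- Female share of consenters: f_c = fR / (fR + 1 − f)
- Bias = (f_c − f) × (pF − pM)

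The bias is zero if R = 1 or pF = pM.

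**Inputs.** The documents give no consent rate by sex, no ID prevalence by sex, and no figure for the female share beyond donors being mostly male. All three are assumed. With f = 0.30:

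| R | f_c | pF − pM | Bias (points) |
|---|---|---|---|
| 1.2 | 0.36/1.06 = 0.340 | 0.10 | +0.4 |
| 1.25 | 0.375/1.075 = 0.349 | 0.25 | +1.2 |
| 1.5 | 0.45/1.15 = 0.391 | 0.25 | +2.3 |
| about 1.9 | 0.450 | 0.25 | +3.75 |
| 0.5 | 0.15/0.85 = 0.176 | 0.25 | −3.1 |

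The fourth row takes ID as 50% in women and 25% in men. The estimate is 0.45 × 0.50 + 0.55 × 0.25 = 36.25%, and the truth is 0.30 × 0.50 + 0.70 × 0.25 = 32.5%. The ratio it needs is (0.45/0.55)/(0.30/0.70) = 1.91. The last row shows that the sign depends on which sex consents more.

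**Coverage in the +3.75 case, one stratum.** SE = √(0.3625 × 0.6375/146) = 0.0398. Bias/SE = 0.0375/0.0398 = 0.94. Coverage of a nominal 95% interval = Φ(1.96 − 0.94) − Φ(−1.96 − 0.94), about 84%. The bias is about half of that stratum's own 7.8-point margin (1.96 × 0.0398).

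**Coverage in the +3.75 case, overall estimate.** Suppose both strata have the same prevalence and the same shift. With deferral share q, SE = √((q² + (1−q)²) × 0.3625 × 0.6375/146).

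- q = 0.33: SE = 0.0297, bias/SE = 1.26, coverage about 76%
- q = 0.50: SE = 0.0281, bias/SE = 1.33, coverage about 73%
- q = 0.53: SE = 0.0282, bias/SE = 1.33, coverage about 73%

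The 33–53% quoted in SAP 2.4 serves here only as an illustrative range for q. The protocol's Problem Statement describes it as a share of deferred donors.

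**Does the proposed weighting remove it?** Take q = 0.43, female share 0.4 among those who fail and 0.2 among those who pass, and ID in women/men of 0.80/0.50 (fail) and 0.40/0.15 (pass).

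- Truth: 0.43 × 0.62 + 0.57 × 0.20 = 38.1%
- SAP estimator: 34.9% at R = 0.5, 40.4% at R = 1.5 and 42.2% at R = 2
- Copper sulphate by sex weighting: 38.1% in each case, because it uses the attenders' sex mix in place of the consenters'

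**The case against.** The strongest objection concerns evidence. The bias needs a sex gap in ID within a copper sulphate stratum. The background figures are for anaemia, come from two general-population sources, and do not condition on the copper sulphate result. The test already uses sex-specific cut-offs (13.0 g/dL for men, 12.0 g/dL for women), so part of the marginal gap may be absorbed; it could shrink, persist or reverse. The iron-store figure for women has no male comparator. No passage suggests that women consent at nearly twice the male rate. All of this stands, and it makes the size an assumption.

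A reader might infer that the planned estimates are biased, or that their intervals will cover about 75% of the time. The documents support neither. Whether any bias exists depends on two quantities that they do not give. A coverage near 75% applies only to the overall estimate, with a strong consent imbalance and the same shift in both strata. For a single stratum under the same inputs it is about 84%.

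It is also fair that the word unbiased in SAP 1.2 is aimed at the unequal approach by copper sulphate result, and that reliance on ignorable consent is common in consent-based prevalence work. The table by consent in SAP 2.6 would show an imbalance in sex, and the SAP can be updated until database lock. But neither provision commits to an adjustment, and SAP 7.1 goes further by claiming consistency for the whole population.

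Finally, the remedy is partial. Age and donor type are recorded too, and unrecorded factors remain.

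**Conclusion.** The point holds in conditional form. The unbiasedness in SAP 1.2 and the consistency in SAP 7.1 follow only if consent is unrelated to iron status within each copper sulphate stratum, and neither section says so. If consent and ID/IDA prevalence both differ by sex within a stratum, the planned estimator can be biased, and weighting on deferral does not remove it.

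Modest assumptions give a shift well inside the stated margin: under half a point at a ratio of 1.2 with a 10-point gap. Only a strong imbalance with a large gap brings it close to 4 points and costs material coverage. The wording needs correcting whatever the size. The change of estimator is worth making because the variable is already collected and the planned method extends to it directly. This is a correctable weakness in a secondary estimate of a pilot study.

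**What to change.** In SAP 7.1, post-stratify on copper sulphate result by sex (four cells). Take the cell shares from first-time donors in the deferment study (voluntary first-time donors, if that is who enrols) and draw them from a Dirichlet posterior. Draw the ID and IDA probability in each cell from a beta posterior, and combine the draws as already planned.

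In SAP 1.2 and 7.1, replace the unconditional claims with a statement that the estimates are unbiased or consistent only if consent does not depend on iron status given sex and copper sulphate result.

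The cost is SAP wording and a small code change, with no new data. The downside is smaller cells, especially for women, and somewhat wider intervals. Selection on other or unrecorded factors is not corrected, and the report should say so.
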